**Pegloticase:**

All subjects who meet the inclusion/exclusion criteria and tolerate oral MTX 15 mg weekly during the MTX Run-in Period will receive pegloticase at a dose of 8 mg administered IV every 2 weeks for a total of 12 infusions from Day 1 through Week 22 inclusive (Pegloticase + MTX Period). The date and start and stop time of infusion will be recorded. Subjects will not be fasting on the day of infusion and will be encouraged to have a snack or normal meal before or after the infusion.

All subjects will receive standardized prophylactic treatment to reduce the risk of acute gout flares, beginning  $\geq$ 1 week before the first dose of pegloticase and continuing throughout the pegloticase treatment per American College of Rheumatology guidelines [[Khanna D et al. 2012](#)].

Standardized IR prophylaxis consisting of pre-treatment with an antihistamine, acetaminophen and a corticosteroid will accompany each infusion.

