#### **Duration of Treatment and Follow-up:**

**Screening:** Up to 35 days prior to the Pegloticase + MTX Period.

**MTX Run-in Period (Week – 4 to Day 1):** 4 weeks of MTX dosing prior to initial pegloticase dose.

**Pegloticase + MTX Period (Day 1 through Week 24):** 24 weeks (infusion visits every 2 weeks) plus the End-of study/Early Termination Visit (Week 24)

**Week 24/End-of-study/Early Termination Visit:** Week 24 or earlier if the subject withdraws consent to participate in the study.

**End of Pegloticase Infusions Visit (if applicable):** If the subject discontinues pegloticase treatment prior to infusion Week 22, such as due to the sUA Discontinuation Criteria, the subject will complete this visit within approximately 2 weeks of the last infusion. Subjects will continue in study for Follow-Up visits, including the 30-day Follow-Up Email/Phone call, Week 24/End of Study/Early Termination and 3 Month Post-Treatment Follow-up Visits.

**Safety Follow-up Visit:** All subjects will receive a safety Follow-up phone call/e-mail/visit approximately 30 days after the last dose of pegloticase to assess if any AE/SAE's have occurred and to confirm if any previous AE/SAEs have resolved. Subjects who receive at least one dose of MTX and are females of childbearing potential, will receive a safety Follow-up phone call/e-mail/ approximately 30 days after the last dose of MTX to verify at least one ovulatory cycle has occurred after the last dose of MTX. If the subject has not ovulated, a urine pregnancy test will be performed. Subjects who receive at least one dose of MTX and are non-vasectomized males, a phone/e-mail/site visit inquiry will be conducted 3 months after MTX discontinuation regarding partner pregnancy (inquiry can occur during the 3-month Post-Treatment Follow-up). If the subject discontinues treatment but continues in the study, then this Follow-up visit may be replaced by a scheduled study visit.

**3-Month Post-Treatment Follow-up Visit:** All subjects will be followed for a minimum of 3 months following the last infusion, with follow-up after Week 24 as warranted.

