### **9.6.1.8 Clinical Laboratory Safety Tests**

Blood (for hematology and clinical chemistry) will be collected at Screening, Week -2, prior to the pegloticase infusion on Day 1 and at the Week 2, 6, 14 and 22 Visits, the End -of -Pegloticase -Infusions Visit (if applicable), the Week 24/End -of -Study/Early Termination Visit and 3 -month Post -Treatment Follow -up Visit.

Urine (for albumin: creatinine ratio) samples will be collected at Screening, prior to the pegloticase infusion on Day 1 and at the Week 2, Week 6, 14 and 22 Visits, the End -of -Pegloticase -Infusions Visit (if applicable) and Week 24/End -of -Study/Early Termination Visit.

Safety laboratory assessments will include:

3. Hematology: complete blood count with differential (hemoglobin concentration, hematocrit, erythrocyte count, platelet count, leukocyte count and differential leukocyte count);
4. Chemistry: albumin, transaminases (aspartate aminotransferase, alanine aminotransferase), alkaline phosphatase, total bilirubin, creatinine (including calculation for eGFR calculated by the Modification of Diet in Renal Disease [MDRD] study equation :  $175 \times (S_{cr}[\text{mg/dL}])^{-1.154} \times (\text{age})^{-0.203} \times (0.742 \text{ if female}) \times (1.212 \text{ if African American})$  or  $175 \times (S_{cr}[\mu\text{mol/L}])^{88.4}^{-1.154} \times (\text{age})^{-0.203} \times (0.742 \text{ if female}) \times (1.212 \text{ if African American})$ ), glucose, sodium, potassium, calcium, chloride, total protein, blood urea nitrogen and human chorionic gonadotropin (at the Screening Visit and the Week 24/End of Study/Early Termination Visit for all female subjects of childbearing potential); and
5. Urine: albumin: creatinine ratio and human chorionic gonadotropin (for all female subjects of childbearing potential).

Safety laboratory samples will be analyzed by the central laboratory. Samples will be collected for analysis at the local laboratory, if needed.

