#### 3.1.1 Reporting Conventions

The formats for the tables, listings, and figures described in this SAP will be provided in a companion document. Changes to the formats of these reports that are decided after the finalization of the SAP will not require an amendment. In addition, any additional supportive or exploratory analyses requested after SAP approval will not require amendment of the SAP. These additional analyses will be described in the CSR.

Study data from the electronic case report forms as well as relevant derived variables will be provided in subject data listings. An indication of specific listings for each data type may be indicated in the text of subsequent SAP sections. Data listings supplied as part of the CSR will be sorted by study center number concatenated with subject number, assessment dates, and time point, if collected.

The following conventions will be applied to all data presentations and analyses:

Continuous variables will generally be summarized by the number of subjects, mean, standard deviation, median, minimum, and maximum. Unless otherwise specified, the minimum and maximum values will be displayed to the same number of decimal places as the raw data, the mean and median will be presented to one extra decimal place compared to the raw data, and the standard deviation will be displayed to two extra decimal places compared to the raw data

Categorical variables will be summarized using frequencies and percentages within each category. Unless otherwise specified, the percentage will be presented in parentheses to one decimal place. Frequency and percentage values of 0 will be presented as '0' rather than '0 (0)'.

Unless otherwise specified, time to event data will be reporting using weeks as the timescale.

All summary tables will include the analysis set sample size (i.e., number of subjects).

Date variables will be formatted as DDMMYY for presentation.

Unless otherwise specified, confidence intervals (CI) will be based on two-sided 95% confidence.

If multiple assessments occur at a given post-baseline time point, the latest value will be used.

There will be no statistical testing to make an inference.

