Pegloticase + MTX	Day 1	1	1
	Week 14	99	2 – 127
	Week 22	155	128 – 162
	Week 24	169	≥ 163

In the event that an End of Study/ET or End of Pegloticase visit is reassigned to a visit for which the subject has scheduled data collected, the data from the nominal scheduled visit will take precedence and the data from the End of Study/ET or End of Pegloticase visit will not be summarized. If the End of Study/ET or End of Pegloticase visit maps to a visit where the assessment was scheduled to be collected, and a scheduled collection is not available at that time point, the End of Study/ET or End of Pegloticase visit data will be summarized in the scheduled visit assessment.

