### 3.6.4 Laboratory Tests

Laboratory test results, including urine albumin: creatinine ratio, will be summarized by treatment period, infusion duration group, and study visit. For summaries of visits during the

Pegloticase + MTX Period, only data collected within 30 days (inclusive) after the last dose of MTX or pegloticase will be included. Results from the 3 Month Follow-up visit will also be summarized.

Shift-from-MTX baseline tables for laboratory parameters by Common Terminology Criteria for Adverse Events (CTCAE) grade will be presented. For tests where the CTCAE criteria are available, grade will be assigned programmatically, and shift tables will be based on the derived CTCAE grade. The CTCAE version 4.03 will be used for these summaries. Laboratory test results without established CTCAE grading criteria will also be classified relative to the normal reference range (normal, low, or high) and summarized as shift tables.

Laboratory summaries will be provided for both safety (both treatment periods) and ITT analysis sets (MTX Run-in Period only). Shift tables and change from baseline will be reported using the following baseline visits and periods:

- MTX Run-in Period: summarized for ITT analysis set using MTX baseline
- MTX Run-in Period and Pegloticase + MTX Period: summarized for safety analysis set using MTX baseline
- Pegloticase + MTX Period: summarized for safety analysis set using pegloticase baseline

A summary of elevated liver function test values, Hy's law, and subjects meeting MTX intolerance criteria (hematology only) will be provided for the safety analysis set by visit and overall for the MTX Run-in Period and the Pegloticase + MTX Period. Analyses of liver function tests and MTX intolerance criteria (hematology only) will also be done for the ITT for only the MTX Run-in period.

- alanine aminotransferase > ULN, 2xULN, 3xULN, 5xULN, 10xULN, and 20xULN
- aspartate aminotransferase > ULN, 2xULN, 3xULN, 5xULN, 10xULN, and 20xULN
- alkaline phosphatase  $\geq$  1.5xULN, 2.5xULN, and 3xULN
- total bilirubin  $\geq$  1.5xULN, 2xULN, and 3xULN

Hy's law:

- (alanine aminotransferase or aspartate aminotransferase > 3xULN) and total bilirubin  $\geq$  2xULN on the same date
- (alanine aminotransferase or aspartate aminotransferase > 3xULN) and total bilirubin  $\geq$  2xULN and alkaline phosphatase < 2xULN on the same date

MTX intolerance criteria (hematology):

- WBC  $<$  3.5  $\times$  10^9/L

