## 3.7 Other Analyses

### 3.7.1 C-Reactive Protein

C-Reactive protein will be summarized by infusion duration group for the safety analysis set during the Pegloticase + MTX Period. The summary will include the change from pegloticase baseline. End of pegloticase and end of study results will be given their own timepoint with no visit windowing.

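### SAP 3.1.5 leaves End of Pegloticase safety labs out of the summary tables when the mapped window already holds a scheduled sample, which affects 2 to 5 of the 11 possible early stopping points in the visit timings checked

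*SAP*

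**What the plan says.** SAP 3.1.5 applies its windowing to all analyses. Table 2 gives the windows for laboratory assessments and urine albumin:creatinine ratio: Week 2 covers Days 2–29, Week 6 Days 30–71, Week 14 Days 72–127, Week 22 Days 128–162, and Week 24 Day 163 onward. The End of Study/Early Termination and End of Pegloticase visits are mapped into these windows by study day. If the subject already has scheduled data for that visit, the scheduled data win and "the data from the End of Study/ET or End of Pegloticase visit will not be summarized". If instead "a scheduled collection is not available at that time point, the End of Study/ET or End of Pegloticase visit data will be summarized", the stopping-visit result fills the empty slot.

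Protocol 9.6.1.8 schedules on-treatment hematology and chemistry at Day 1 "and at the Week 2, 6, 14 and 22 Visits", and also at the End of Pegloticase visit.

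Two other SAP rules bear on the same samples. For visits in the Pegloticase + MTX Period, SAP 3.6.4 says "only data collected within 30 days (inclusive) after the last dose of MTX or pegloticase will be included". SAP 3.1.1 has a general rule for duplicates: "If multiple assessments occur at a given post-baseline time point, the latest value will be used". C-reactive protein is treated differently. In SAP 3.7.1, "End of pegloticase and end of study results will be given their own timepoint with no visit windowing".

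SAP 3.6.4 reports liver-test thresholds, Hy's law and MTX hematology-intolerance criteria both per visit and overall. It does not define which records feed the overall counts.

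**The concern.** The protocol asks for a safety sample when pegloticase stops. For a subject who stops early, that sample is normally the last laboratory value obtained on or just after treatment. On-treatment labs are sparse, so the Table 2 windows are wide, and a stopping visit often falls in a window whose scheduled sample was drawn weeks before. The precedence rule then keeps the older value and leaves out the newer one. Whether this happens depends on the week of stopping, not on what the sample shows.

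At stake are the by-visit laboratory summaries and, depending on how the overall counts are built, the number of subjects reported as crossing a liver threshold, meeting Hy's law or meeting the MTX hematology criteria. The primary endpoint, infusion reactions, is not affected.

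**Working it through.** **Inputs.** Windows and target days (15, 43, 99, 155, 169) are from SAP Table 2, and lab visits are from Protocol 9.6.1.8. Pegloticase is given "every 2 weeks for a total of 12 infusions from Day 1 through Week 22 inclusive" (protocol synopsis, dose regimen). The End of Pegloticase visit applies "If the subject discontinues pegloticase treatment prior to infusion Week 22" (synopsis, duration of treatment), so the last infusion can be at Day 1 or Weeks 2 to 20, which gives 11 stopping points. Schedule of Assessments footnote 3 puts the visit within 2 weeks of the last infusion, and the synopsis says approximately 2 weeks. The note to Protocol Figure 9.1 allows ±3 days around each visit.

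**Step 1: reproduce Table 2.** The upper limits are midpoints between target days: (15+43)/2 = 29, (43+99)/2 = 71, (99+155)/2 = 127, (155+169)/2 = 162. All match.

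**Step 2: map each stopping point.** An on-target infusion at Week w falls on Day 7w+1. The visit is placed 1 to 14 days later. A value is omitted if the scheduled sample of its window was due on or before the last infusion.

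| Last infusion | Day | Visit day (+1 to +14) | Window | Scheduled sample already taken? | Omitted minus kept, at +14 |
|---|---|---|---|---|---|
| Day 1 | 1 | 2–15 | Week 2 | No | – |
| Week 2 | 15 | 16–29 | Week 2 | Yes, Day 15 | 14 days |
| Week 4 | 29 | 30–43 | Week 6 | No | – |
| Week 6 | 43 | 44–57 | Week 6 | Yes, Day 43 | 14 days |
| Week 8 | 57 | 58–71 | Week 6 | Yes, Day 43 | 28 days |
| Week 10 | 71 | 72–85 | Week 14 | No | – |
| Week 12 | 85 | 86–99 | Week 14 | No | – |
| Week 14 | 99 | 100–113 | Week 14 | Yes, Day 99 | 14 days |
| Week 16 | 113 | 114–127 | Week 14 | Yes, Day 99 | 28 days |
| Week 18 | 127 | 128–141 | Week 22 | No | – |
| Week 20 | 141 | 142–155 | Week 22 | No | – |

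The result is 5 of 11 omitted, at every lag from 1 to 14 days.

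**Step 3: move the visit past the edge.** At 14 days, stops after Weeks 2, 8 and 16 land on Days 29, 71 and 127, each the last day of its window. At 15 days they land on Days 30, 72 and 128, in the next and still empty window, and are kept. Weeks 6 and 14 stay inside their windows even at 21 days (Day 64 against a limit of 71, and Day 120 against 127). The count is then 2 of 11. A 14-day visit after a last infusion given 1 to 3 days late has the same effect. For example, a Week 2 infusion on Day 16 puts the visit on Day 30. The figures of 5 and 2 belong to these scenarios and are not bounds over every combination of visit timings.

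**Step 4: can Week 24 labs fill the gap?** The latest affected stop is Week 16, Day 113. Protocol 9.4.3.1.1 stops MTX with pegloticase, so the cut-off is Day 113+30 = 143. Even if MTX ran 14 days longer (an assumption), it would be Day 127+30 = 157. Week 24 is Day 169, or Day 166 with the visit allowance. So Week 24 labs fall outside the limit for all five stops.

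**Step 5: direction.** A subject counts toward an overall threshold if any included value meets it. Taking values out of the included set can only lower that count or leave it unchanged. The by-visit slot still holds the older scheduled value, so the direction of effect on by-visit means is not known.

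**Step 6: after the change.** With a separate End of Pegloticase time point, 0 of 11 stopping points lose their value from the tables.

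**The case against.** The strongest reply is that nothing disappears. SAP 3.1.1 puts study data in subject listings. SAP 3.6.4 lists subjects who meet the liver, Hy's law or MTX-intolerance criteria with their results. A laboratory change the investigator judges clinically significant is an adverse event under Protocol 9.6.1.2.1.1 and is summarized through 30 days after the last dose under SAP 3.6.3.1. This stands: a reader who infers that the data are lost goes too far. But listings and adverse event tables do not correct a laboratory incidence table.

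Second, the SAP does not confine the overall counts to windowed records, and its Hy's law definition, which needs results on one date, fits evaluation record by record. This also stands. A reader might infer that overall incidence is certainly biased down, but the text supports that only under one reading of a silent point.

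Other stronger readings lack support:

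- That about 45% of early stoppers are affected. This turns 5 of 11 calendar slots into a share of subjects, and the documents give no distribution of stopping times.
- That early stoppers carry more hepatic or hematologic abnormality. Protocol 9.4.3.1 lists several reasons for stopping, including lack of efficacy and adverse events, and Protocol 9.5.7.3.2.2 handles MTX-related laboratory findings through MTX dosing. No passage shows the excess.
- That a normal repeat test replaces an abnormal one under SAP 3.1.1. The only explicit windowing rule for unscheduled results is for sUA (SAP 3.1.7), and nothing assigns an unscheduled safety lab to a scheduled visit. For a stopping sample in an occupied window, the latest-value rule would favour the later sample.

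Finally, C-reactive protein is an exploratory biomarker drawn at few visits, so SAP 3.7.1 shows that a separate time point is workable, not that safety labs must follow it.

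**Conclusion.** The point holds in a limited form. The omission from summaries is a stated rule. It covers 5 of 11 possible stopping points when the visit falls within 14 days of an on-target last infusion, and 2 of 11 when it runs past the window edge. These are stopping points, not proportions of subjects. The tables then show a value 14 or 28 days older than the omitted one (visit at 14 days), with no later on-treatment value to replace it.

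The consequence for by-visit tables is definite. The consequence for overall liver, Hy's law and MTX-hematology counts is conditional on those counts using windowed records only. If they do, the error runs in one direction. Its size cannot be stated from the documents. SAP 3.1.1 and 3.1.5 also give opposite answers for the same pair of samples. The matter should be settled in the SAP, but it does not threaten the primary analysis.

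**What to change.** Make three wording changes, which SAP 3.1 would document as an SAP amendment if made before database lock:

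1. In SAP 3.1.5, exempt hematology, chemistry and urine albumin:creatinine ratio from the precedence rule, and present End of Pegloticase/Early Termination as its own time point, as SAP 3.7.1 does.
2. In SAP 3.6.4, state that the overall threshold, Hy's law and MTX-intolerance counts use every post-baseline value within the 30-day limit, including End of Pegloticase/Early Termination and unscheduled results, and that a subject counts if any value meets the criterion.
3. Reconcile the latest-value rule in SAP 3.1.1 with the scheduled-visit precedence in 3.1.5, saying which governs safety labs.

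The cost is table programming, and abnormality counts may come out slightly less favourable. No visit, sample or clinical rule changes.

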##### **9.4.3.1.1 Study considerations for subjects ending pegloticase infusions prior to 24 weeks**

- Methotrexate, along with folic acid, will be discontinued at the time of cessation of pegloticase infusions prior to Week 24.
- All subjects will complete the End of Pegloticase Infusions Visit and should be encouraged to remain on study and attend all Follow-Up visits, including the 30-day Follow-up Email/Phone call, Week 24/End of Study/Early Termination and 3 Month Post-Treatment Follow-up Visits barring withdrawal of consent from study participation.
- Activities related to pre/post infusion monitoring or medication dispensation will not be completed once a subject has stopped pegloticase infusions. These activities include:
  - MTX compliance/reconciliation

- IR prophylaxis
- IR prophylaxis compliance
- Folic acid compliance
- Pegloticase infusion
- Pegloticase PK sampling
- Pre-infusion MTX Polyglutamate sampling
- MTX drug/dispensation related items

Post-Treatment Follow-up:

The intent is to obtain at least 3 months of follow up on each subject after cessation of pegloticase infusions. If the subject ends treatment early but remains in the study and the 3-month Post-Treatment Follow-up Visit occurs prior to Week 24, the 3-month Post-Treatment Follow-up Visit will be adjusted accordingly based on the timing of the last treatment.

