### 3.1.5 Visit Windowing

For all analyses, data will be summarized according to the scheduled visit and time points as outlined in the protocol and by the visit denoted on the electronic case report form (eCRF). The reference date associated with each visit is collected on the Visit Date eCRF page. Further, the End of Study/Early Termination (ET) visit and the End of Pegloticase Infusion Visit will be windowed to a visit based on the study day of occurrence relative to the target day of each scheduled visit according to Tables 1-8 below.

**Table 1: Visit Windows for Assigning End of Study/ET and End of Pegloticase Visits to a Scheduled Visit (Vital Signs, sUA)**

Study Period	Visit	Target Day a	Window for Reassignment to Scheduled Visit (days)
Pegloticase + MTX	Day 1	1	1
	Week 2	15	2 – 22
	Week 4	29	23 – 36
	Week 6	43	37 – 50
	Week 8	57	51 – 64
	Week 10	71	65 – 78
	Week 12	85	79 – 92
	Week 14	99	93 – 106
	Week 16	113	107 – 120
	Week 18	127	121 – 134
	Week 20	141	135 – 148
	Week 22	155	149 – 162
	Week 24	169	≥ 163

a Study days in the Pegloticase + MTX Period will be calculated relative to the first dose of Pegloticase.

**Table 2: Visit Windows for Assigning End of Study/ET and End of Pegloticase Visits to a Scheduled Visit (Laboratory Assessments and Urine Albumin: Creatinine Ratio)**

Study Period	Visit	Target Day a	Window for Reassignment to Scheduled Visit (days)
Pegloticase + MTX	Day 1	1	1
	Week 2	15	2 – 29
	Week 6	43	30 – 71
	Week 14	99	72 – 127
	Week 22	155	128 – 162
	Week 24	169	≥ 163

a Study days in the Pegloticase + MTX Period will be calculated relative to the first dose of Pegloticase.

[figure not shown]
**Table 3: Visit Windows for Assigning ET and End of Pegloticase Visits to a Scheduled Visit (Pegloticase PK and Antibody testing)**

Study Period	Visit	Target Day a	Window for Reassignment to Scheduled Visit (days)
Pegloticase + MTX	Day 1	1	1
	Week 2	15	2 – 29
	Week 6	43	30 – 64
	Week 12	85	65 – 113
	Week 20	141	114 – 155
	Week 24	169	≥ 156

a Study days in the Pegloticase + MTX Period will be calculated relative to the first dose of Pegloticase.

**Table 4: Visit Windows for Assigning ET and End of Pegloticase Visits to a Scheduled Visit (Pre-infusion MTX Polyglutamate PK)**

Study Period	Visit	Target Day a	Window for Reassignment to Scheduled Visit (days)

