Concentrations of MTX polyglutamate are measured for 5 active metabolites (MTX-PG1, MTX-PG2, MTX-PG3, MTX-PG4, MTX-PG5). The summary of individual 5 MTX polyglutamate values, PG1-2 (i.e., PG1 + PG2), PG3-5 (i.e., PG3 + PG4 + PG5), PG4-5 (i.e., PG4 + PG5), and total PG1-5 (i.e., PG1 + PG2 + PG3 + PG4 + PG5) over time for all mITT subjects, as well as by Month 6 sUA responders and Month 6 sUA non-responders will be provided. All concentrations BLQ are excluded from the analysis summaries. When calculating the sum over MTX-PGs, values of '<5' count as 0 in the sum.

A plot of the mean total PG1-5, and individual 5 MTX polyglutamate mean values over time will be provided for the mITT set by Month 6 sUA response status (responder vs. non-responder) for each infusion duration group.

A listing of MTX polyglutamate concentrations will be provided, showing the subject, treatment, visit, collection date and time, study day relative to first MTX treatment date, and the 5 MTX polyglutamate values along with total MTX polyglutamate values (PG1-5).

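### When no scheduled Week 14 sample exists, SAP Table 4 labels end-of-treatment MTX polyglutamate samples from as early as Day 2 as Week 14, and nearly all of these belong to Month 6 non-responders

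*SAP*

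**What the plan says.** Protocol 9.6.5 and SAP 1.4.3 schedule MTX polyglutamate samples on Day 1, at Weeks 14 and 22, at the End of Pegloticase Infusions Visit if there is one, and at Week 24. SAP 3.1.5, Table 4, assigns End-of-Pegloticase and early-termination samples to scheduled visits: Day 1 to Day 1, Days 2–127 to Week 14, Days 128–162 to Week 22, and Day 163 onward to Week 24. The footnote to the companion tables fixes the origin: "Study days in the Pegloticase + MTX Period will be calculated relative to the first dose of Pegloticase".

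Two sentences below Table 4 govern its use. If the subject has data from the scheduled visit, "the data from the nominal scheduled visit will take precedence". If the visit maps to one where the assessment was due "and a scheduled collection is not available at that time point", then "the End of Study/ET or End of Pegloticase visit data will be summarized in the scheduled visit assessment".

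SAP 3.5.1 summarizes polyglutamates over time for all mITT subjects, "as well as by Month 6 sUA responders and Month 6 sUA non-responders will be provided", and plots the means by response status within each infusion duration group.

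Protocol 9.4.3.1.1 says: "Methotrexate, along with folic acid, will be discontinued at the time of cessation of pegloticase infusions prior to Week 24". The same section lists pre-infusion polyglutamate sampling among the activities that end when infusions end. For C-reactive protein, SAP 3.7.1 takes another route: "End of pegloticase and end of study results will be given their own timepoint with no visit windowing".

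**The concern.** The Week 14 window is wide on one side only because nothing is sampled between Day 1 and Week 14. A value from a subject who stopped in the second month can therefore be tabulated and plotted as a Week 14 value.

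This does not fall evenly on the two groups being described. Stopping before Week 14 both triggers the relabelling and, in nearly every case, makes the subject a Month 6 non-responder. A lower non-responder mean at Week 14 could then reflect shorter MTX exposure, or a sample taken after MTX had stopped. A reader of the plot could take it as a sign that low polyglutamate levels go with loss of response.

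**Working it through.** **Reproducing the window.** Target day = 7 × week + 1, so Weeks 14, 22 and 24 are Days 99, 155 and 169. Each upper limit is the midpoint of neighbouring targets: (99 + 155)/2 = 127 and (155 + 169)/2 = 162. Each lower limit is the day after the previous window ends, and the Day 1 window is Day 1 alone. This gives 1, 2–127, 128–162 and ≥163, exactly as in Table 4. The Week 14 window thus reaches 99 − 2 = 97 days below target and 127 − 99 = 28 days above it. The same rule gives Week 14 as Days 93–106 in Table 1 and Days 72–127 in Table 2, where neighbouring samples are closer.

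**Who is relabelled.** Under Protocol 9.3 and 9.4.3, subjects taken off pegloticase attend follow-up visits only, so a stop before Week 14 leaves no scheduled Week 14 sample and the precedence rule has nothing to act on.

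**Which response group they fall in.** Under SAP 3.4.2.1, subjects meeting the sUA discontinuation criterion are non-responders, as are those with sUA from fewer than two visits in Month 6. A subject who stopped early for another reason has only Week 24 as a scheduled visit in Month 6. That subject could be a responder only with a second value, from an unscheduled draw or a follow-up visit that happens to fall in that month.

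**Exposure at the relabelled samples.** MTX starts 4 weeks before Day 1, so a true Week 14 sample is 4 + 14 = 18 weeks after MTX start. The sUA rule counts from Week 2, so the earliest stop is Week 4. The End of Pegloticase visit falls within about 2 weeks of the last infusion; 2 weeks is used here.

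| sUA-rule stop | Sample day | Weeks since MTX start | Share of 18 weeks | Weeks of MTX if it ended at the last infusion |
|---|---|---|---|---|
| Week 4 | 29 | 8 | 44% | 6 |
| Week 6 | 43 | 10 | 56% | 8 |
| Week 8 | 57 | 12 | 67% | 10 |
| Week 10 | 71 | 14 | 78% | 12 |
| Week 12 | 85 | 16 | 89% | 14 |

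A stop for another reason after the Day 1 infusion gives a sample by about Day 15, after roughly 4 to 6 weeks of MTX. A stop at Week 14 gives a sample near Day 99, which is labelled correctly. Stops at Weeks 16 and 18 (Days 113 and 127) fall in the window, but an existing Week 14 sample takes precedence. Stops at Weeks 20 and 22 (Days 141 and 155) map to Week 22.

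**Share of non-responder Week 14 values affected.** Let f be the share of non-responders who stop before Week 14 and c the share of those who give an end-of-treatment sample. Assume all other non-responders have a scheduled Week 14 sample. Then share = f·c / (f·c + 1 − f).

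- With c = 1 the share equals f. With c = 0.5 it runs from 5% (f = 0.1) to 82% (f = 0.9).
- It exceeds one half only if f > 1/(1 + c): 0.50 for c = 1, about 0.57 for c = 0.75, about 0.67 for c = 0.5.
- If every non-responder stopped by the sUA rule, evenly over the ten visits from Week 4 to Week 22, five of the ten precede Week 14: 50%. If only half stopped by that rule: 25%. Both take c = 1.

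**Effect on mean exposure in the Week 14 row.** With stops spread evenly over Weeks 4 to 12, relabelled samples average (8 + 10 + 12 + 14 + 16)/5 = 12 weeks. With c = 1 the non-responder mean is 12f + 18(1 − f): 17.4 weeks at f = 0.1, 15.0 at f = 0.5 and 12.6 at f = 0.9.

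**The case against.** The precedence rule is a real limit. Anyone with a scheduled Week 14 sample is unaffected, including subjects who stop at Week 16 or 18, so it would be wrong to infer that every end-of-treatment sample in Days 2–127 is relabelled. The rule does not help subjects who stop before Week 14.

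A reader might also infer that the non-responder Week 14 values come mostly from early samples. The documents do not support that: they give no distribution of stopping times and no count of non-responders. Late failures, and other non-responders who reach Week 14, contribute true Week 14 values.

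Nor is exposure always much shorter. That fits stops at Weeks 4 to 6 (44% to 56% of 18 weeks), not a stop at Week 12 (89%). MTX is planned 1 to 3 days before each infusion, so a subject found to meet the sUA rule at a visit will often have dosed recently. The off-drug element is possible, not certain.

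Whether the sample exists is itself unclear. Protocol 9.4.3.1.1 ends polyglutamate sampling with infusions, while Protocol 9.6.5 and SAP 1.4.3 collect it at the End of Pegloticase visit.

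Finally, little depends on the result. Polyglutamate level is not among the endpoints visible in the SAP, no inferential testing is planned, and the listing shows collection date and study day from first MTX dose. All of this stands, and it limits the importance of the point. It does not make the Week 14 label correct for the subjects concerned.

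**Conclusion.** The point holds as a labelling fault in a descriptive analysis. Where no scheduled Week 14 sample exists, samples from as early as Day 2 are reported as Week 14, and nearly all come from Month 6 non-responders. For sUA-rule stops at Weeks 4 to 12 they represent about 8 to 16 weeks since MTX start instead of 18, with up to 2 weeks less actual dosing if MTX ended at the last infusion. These figures assume the End of Pegloticase visit takes place 2 weeks after the last infusion.

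The share of affected values cannot be fixed from the documents; the 50% and 25% figures are illustrations under stated assumptions. The difference in concentration cannot be sized either, because neither document gives accumulation or washout rates. Converting through an assumed half-life would be guesswork. Applying two weeks of washout on top of the full 8 weeks of accumulation would count the same two weeks twice.

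It would also go too far to say that the plan creates a false link between MTX levels and response. The plan makes no such inference; the risk lies in how the table and plot are read. No primary or secondary endpoint is affected. This is a cheap improvement, not a threat to the trial's conclusions.

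**What to change.** In SAP Table 4, narrow the Week 14 window and add one sentence reporting End-of-Pegloticase and early-termination polyglutamate samples outside it as their own time point, as SAP 3.7.1 does for C-reactive protein.

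- Days 93–106, as in Table 1, would exclude all the sUA-rule stops tabulated above.
- Days 72–127, as in Table 2, would exclude those up to about Week 10 (Day 71, subject to the ±3-day visit tolerance) and keep a Week 12 stop (Day 85).

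The separate time point would still pool different lengths of MTX exposure, so it corrects the label and does not remove the confounding. A footnote giving the range of weeks since MTX start would make that visible.

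Reconcile Protocol 9.4.3.1.1 with Protocol 9.6.5 and SAP 1.4.3 on whether the End-of-Pegloticase polyglutamate sample is collected.

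The cost is one table row and one sentence in the SAP, a clarification on sampling, and fewer non-responder values at Week 14. No collected data are lost, since the displaced values are still reported.
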